7. PLANNED ANALYSIS

The format of the listings and tables will follow the BI standards "Standards for Reporting of Clinical Trials and Project Summaries" (10).

A separate DMC SAP which describes the analyses required for assessment by the DMC will be produced and handled by the DMC.

The individual values of all patients will be listed. Listings will generally be sorted by country, centre number, patient number and visit (if visit is applicable in the respective listing). AE listings will be sorted by treatment (see Section 7.8.1 below for details). The listings will be contained in Appendix 16.2 (SDL) of the CTR.

The following standard descriptive statistical parameters will be displayed in summary tables of continuous variables:

Ν	number of non-missing observations
Mean	arithmetic mean
SD	standard deviation
Min	minimum
Q1	lower quartile
Median	median
Q3	upper quartile
Max	maximum

For plasma concentrations and some biomarkers, the following descriptive statistics will additionally be calculated:

CV	arithmetic coefficient of variation
gMean	geometric mean
gCV	geometric coefficient of variation

Statistical parameters will be displayed to a defined number of decimal places as specified in the BI standards "Standards for Reporting of Clinical Trials and Project Summaries" (10).

Tabulations of frequencies for categorical data will include all possible categories and will display the number of observations in a category as well as the percentage (%) relative to the respective treatment. Percentages will be rounded to one decimal place. The category missing will be displayed if and only if there actually are missing values. Percentages will be based on all patients in the respective patient set whether they have non-missing values or not.

Note that for the analysis of all data in this trial, the primary approach is to report only those data that fall within the on-treatment period. However, for selected displays of endpoints presented by-visit, additional ouputs which include both on- and off-treatment data will also be produced.

Disposition of the patient population participating in the trial will be summarised for the ES by presentation of the frequency of patients screened, entered, screened but not entered, treated, entered but not treated, who completed planned visit at Week 12, who completed all

doses of trial medication as planned, who completed planned observation time, and who were prematurely discontinued, by reason. Patients who completed trial through the planned visit at Week 12 must not be considered to have discontinued trial at any time prior to the lower bound of the Week 12 time window. The vital status of prematurely discontinued patients at EoO visit will also be summarised. Disposition will be listed by country.

The frequency of patients with iPDs, also summarised by whether or not the iPD led to exclusion from the CAS or FAS, will be presented for the ENTS.

The frequency of patients in each of the different analysis sets will also be presented.

Unless explicitly specified otherwise baseline, for applicable analyses, refers to the last measurement collected prior to the start of administration of the trial treatment.

7.1 DEMOGRAPHIC AND OTHER BASELINE CHARACTERISTICS

Only descriptive statistics are planned for this section of the CTR.

Descriptive statistics will be presented for demographic parameters and baseline characteristics, based on the FAS.

For the continuous variables described below, the following categories will be defined and presented according to the number and percentage of patients in each category:

Variable	Categories
Age	< 50 years 50 to < 65 years 65 to < 75 years ≥ 75 years
Weight	≤70 kg >70 to ≤80 kg >80 to ≤ 90 kg >90 kg
BMI	< 25 kg/m^2 25 to < 30 kg/m^2 $\ge 30 \text{ kg/m}^2$
Time since first diagnosis	≤ 1 year > 1 to ≤ 5 years > 5 to ≤ 10 years > 10 years

 Table 7.1: 1
 Categories for summary of continuous variables

7.2 CONCOMITANT DISEASES AND MEDICATION

Analyses of concomitant diseases and medication will be based on the FAS.

Concomitant diseases will be coded according to the most recent version of MedDRA. Concomitant medication will be coded according to the most recent version of the World Health Organisation – Drug Dictionary.

Characteristics of the trial disease, such as the disease diagnosis and the type of extraintestinal diagnoses which are present at start of the study, as well as the occurrence of any prior surgery for ulcerative colitis will be descriptively summarized. Any changes in the preexisting extra-intestinal diagnoses (improved or worsened) as well as the development of newly diagnosed extra-intestinal diagnoses will be listed.

A medication will be considered concomitant to treatment, if it

- is ongoing at the start of trial treatment or
- starts within the on-treatment period (see Section 6.1 for a definition of treatments and analysis phases).

Concomitant medication use (excluding rescue medication, historical medication for UC and background medication) will be summarised with frequency and percentage of patients by preferred name. Summaries will be presented for concomitant medication taken during the ontreatment period (cf. Section 6.1).

The frequency and percentage of patients with previous medication for UC treatment will be displayed.

The frequency and percentage of patients taking any background medication for UC will be tabulated by type of background therapy; any increases or decreases in dose of these medications during the on-treatment period will also be displayed.

Rescue medication use (including via background medication dose increase defined for purpose of rescue use) on or after Visit 2 and before end of the on-treatment period will be summarised separately.

Concomitant use of non-drug therapies will be summarised with frequency and percentage. Summaries will be presented for concomitant non-drug therapies taken any time during the on-treatment period (cf. Section 6.1).

7.3 TREATMENT COMPLIANCE

Treatment compliance will be summarised overall via total volume infused (as a % of planned) for the FAS using descriptive statistics (N, mean, SD, minimum, median, maximum). For the patients who discontinued the study treatment prematurely only the visits on or before premature discontinuation will be used for the calculation of overall compliance.

The by visit compliance will be listed only.

The number and percentage of patients with the following overall compliance categories will be presented:

• "< 80% of planned",

- "80 to 120% of planned" and
- "> 120% of planned".

7.4 **PRIMARY ENDPOINTS**

The pre-processing of the raw read count values will be conducted as described in Section 7.3 of the CTP. The primary endpoint will be evaluated for the CAS. The analysis will be performed as defined in Section 7.3.1 of the CTP. The FDR adjusted P-value based on the Wald test and the log2 fold change, are used to identify deregulated genes.

Definition of deregulated genes

A gene is defined as deregulated at time point i if the FDR adjusted P-value of the Wald test is below 0.01 and if |fold change (time point i vs. baseline)| \geq 1.3.

The total number of deregulated genes per (post-baseline) time point (V2, V3, V4, V7 and EoT) will be reported.

The following sensitivity analyses may be conducted:

- The number of deregulated genes will be evaluated for the FAS in case this analysis set differs (with regard to RNA analyses) from the CAS
- In case the number of identified deregulated genes is very large (> 5000 deregulated genes at all time points) a smaller threshold for the FDR adjusted P-value will be considered
- In case the number of identified deregulated genes is empty (or includes less than 50 genes at all time points) the 50 genes with the smallest FDR adjusted P-values will be listed per (post-baseline) time point

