3.2 DISCUSSION OF TRIAL DESIGN, INCLUDING THE CHOICE OF CONTROL GROUP(S)

This trial is designed as an open-label, single-arm, phase IIa exploratory trial of BI 655130 in patients with active UC.

The present trial is of exploratory nature and aims to explore the mechanism of action of the 1st in class IL-36R inhibitor in UC. The primary aim of the trial is to evaluate changes in various genetic and epigenetic markers under conditions of IL-36 pathway inhibition and will be compared to the individual baseline values rather than a control group. The comparison between two baseline visits will describe the spontaneous variability in expression of the target genes and markers. The nature of the regulated genes and BMs will shape the subsequent development of BI 655130 in IBD to define potential new endpoints, target indications and BMs to identify responder patient populations. In addition, this trial will include clinical and endoscopic activity evaluations of BI 655130 which may support subsequent trials in achieving clinical proof of concept (PoC) of this potential UC treatment. As shown in the recent proof of concept trial with etrolizumab (R17-0373) in a similar UC population as the one proposed here with BI 655130, the clinical response and remission rates on PBO were very low, probably due to endoscopic screening of patients. Since the patient population in this trial will be similar and endoscopic eligibility criteria have to be met as well, a potential clinical effect is likely to be caused by treatment rather than representing a PBO effect. However, clinical effects are not the primary objective and a clinical PoC study will be conducted in a different properly designed trial. Therefore, a control group is not required for this mechanistic trial comparing gene and BM expression after treatment with baseline, and a single-arm open-label design is appropriate to answer this question.

Since a PoC for BI 655130 is not yet available in UC, the chance of an individual benefit for study participants is difficult to estimate, and thus the sample size and treatment duration was limited to a minimum to achieve the study objectives. The sample size of 10 treated subjects is not based on a power calculation but on coordinating investigator's experience with regard to similar mechanistic studies.

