To get interpretable results several pre-processing steps are needed to correct e.g. for different sequencing depth. For most of these steps the default approach (option) in the DESeq2 software package is used. In detail for the actual study design the following steps are conducted:

- Genes for which the sum of all counts is less than or equal to 1 are excluded.
- Genes with a high pre-treatment variability are excluded from the analysis: A gene is excluded if it meets the regular criteria (>1.5 fold deregulation, FDR adjusted p value <0.01) of being differentially expressed between the two consecutive pre-treatment time points. Hereby, the adjusted P-value is based on the Wald test including only the two pre-treatment time points (i.e. pre-baseline and baseline).
- Read Counts are normalized using the median-of-ratios method of Anders and Huber (R17-0129):

The normalization constants s_{ij} are considered constant within a sample, i.e. $s_{ij} = s_j$. The value s_j is calculated by

 $s_j = \text{median}_{i:K_i^R \neq 0} \frac{K_{ij}}{K_i^R} \text{ with } K_i^R = \left(\prod_{j=1}^m K_{ij}\right)^{1/m}.$

- Estimation of the dispersion parameter α_i : For each gene, an estimate of the dispersion is found which maximizes the Cox Reidadjusted profile likelihood (R17-0128).
- Handling of outlier using Cook's distance (using the default option cooksCutoff = 0.99 in the DESeq2 package): Cook's distance (R17-0126) quantifies how much a single sample is influencing the fitted coefficients for a gene, and a large value of Cook's distance is intended to indicate an outlier count. No changes to the default setting are conducted.

After these pre-processing steps the actual expression analysis can be conducted (see Section 7.3.1)

Adherence to the protocol (such as inclusion/exclusion criteria, times of measurement, compliance with intake of trial medication, treatment dispensing errors, prohibited concomitant medication, completeness and consistency of data) will be checked. Important protocol violations (IPVs) will be identified in the Trial Statistical Analysis Plan (TSAP).

Boehringer Ingelheim		03 Apr 2019
BI Trial No.: 1368-0004		_
c10710598-04	Trial Protocol	Page 60 of 82

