7.3.1 Primary endpoint analyses

For all genes, which are not excluded in the pre-processing step the Wald test (included as the default test for significance testing in the DESeq2 package) is conducted to identify whether this gene is deregulated or not for a certain time point.

Only one baseline value is included in the model, namely the last value before first drug administration, but all post-treatment values. The generalized linear model includes time as additional covariable (and also subject as covariable). So every time point is an additional design matrix element x_{jr} and the model fit leads (for every gene i) to β_{ir} estimates for each time point. To test changes from baseline the contrasts of these β coefficients (or more precisely the difference between post-treatment estimate and baseline) are divided by their estimated standard error, resulting in a z-statistic, which is compared to a standard normal distribution. Hereby the default option *lfcThreshold* = 0 is utilized, meaning a null hypothesis of no difference.

The Wald test results in a P-value and an FDR adjusted P-value for each gene and each posttreatment time point. A gene has a small P-value at a certain time point if there is a significant difference to the pre-treatment estimate, meaning an adjusted mean value clearly lower or higher compared to baseline. The calculation of the FDR adjusted P-value is (by default in the DESeq2 package) based on the Benjamini and Hochberg (P05-11198) approach (*pAdjustMethod* = "*BH*") combined with independent filtering (*independentFiltering* = *TRUE*). The independent filtering is based on the mean of normalized counts as a filtering statistic (R17-0127). A threshold on the filter statistic is found which optimizes the number of FDR adjusted P-values lower than a significance level of *alpha*=0.1 (default setting). In doing so, genes with very low counts at all time points are excluded and no FDR adjusted P-value is reported for these genes.

Beside the FDR adjusted P-value the Wald test calculates for every gene and every time point the difference in fold change compared to the baseline estimate. To get a conservative and stringent approach for the identification of deregulated genes both of these measurements, the FDR adjusted P-value based on the Wald test and the-fold change, are used to identify deregulated genes.

Definition of deregulated genes

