A gene is defined as deregulated at time point i if the FDR adjusted P-value of the Wald test is below 0.01 and if |fold change (time point i vs. baseline)| \geq 1.3.

The total number of deregulated genes per time point will be reported.

Boehringer Ingelheim		03 Apr 2019
BI Trial No.: 1368-0004		
c10710598-04	Trial Protocol	Page 61 of 82

Sensitivity analyses for example evaluation of alternative thresholds for the classification of genes (deregulated vs. not deregulated) will be provided in the TSAP. In particular if e.g. the number of identified deregulated genes is very large a smaller threshold for the FDR adjusted P-value might be considered.

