Description of change	The information regarding the patient diary was changed, as daily reporting of CMs is not included in the current diaries, but the patients have to confirm regular intake of CMs before each visit.	
Rationale for change	To change description of the diaries to clarify that daily reporting of CM intake is not included.	
Section to be changed	6.2.3 Follow up period and Trial Completion	
Description of change	It was added that patients who complete regular treatment can receive long-term treatment in trial 1368-0017. EoO visit would be on the same day as EoT visit.	
Rationale for change	To clarify the time-point of trial completion for patients who enter long-term extension trial 1368- 0017.	
Section to be changed	Section 7.3 PLANNED ANALYSES	
Description of change	It was clarified that the set for the primary evaluation of gene expression includes all patients who completed trial medication and trial throughout EOT visit and who provide at least one evaluable baseline and one evaluable post-baseline biopsy RNA measurement.	
Rationale for change	To clarify description of the patient set for the primary evaluation of gene expression.	
Section to be changed	Section 7.3.1 Primary endpoint analyses	
Description of change	"log2" was removed.	
Rationale for change	To correct an error.	
Section to be changed		

Page 80 of 82

Proprietary confidential information © 2019 Boehringer Ingelheim International GmbH or one or more of its affiliated companies

Description of change		
Rationale for change		
Section to be changed	Section 9.1 PUBLISHED REFERENCES	
Description of change	To add two additional references.	
Rationale for change	To update Section 9.1 regarding two additional references.	
Section to be changed	Section 10.2 MAYO SCORE	
Description of change	In Table 10.2: 1, "granularity" was deleted from footnote d.	
Rationale for change	To correct assessment of modified endoscopic response, according to established criteria for Mayo Score.	
Section to be changed	Section 10.3 EQUIVALENT DOSES OF CORTICOSTEROIDS	
Description of change	"16-Methylprednisolone" was deleted from the table.	
Rationale for change	To correct typographical error.	
Section to be changed	10.3 EQUIVALENT DOSES OF CORTICOSTEROIDS	
Description of change	To add equivalent doses of budenoside.	
Rationale for change	To update table with information for budesonide.	

Number of global amendment	2
Date of CTP revision	18 May 2018
EudraCT number	2017-000100-20

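### The pre-treatment gene filter cuts at more than 1.5-fold, but the only defined rule for a deregulated gene is 1.3-fold, so no-drug shifts in between stay eligible for the primary count

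*SAP*

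**What the plan says.** **Definition.** Protocol 7.3 says that the quantitative criteria for deregulated genes are in 7.3.1. There, and identically in SAP 7.4, the FDR-adjusted P-value must be "below 0.01 and if |fold change (time point i vs. baseline", with the bars closing on a cut of at least 1.3. No other fold cut is defined for the endpoint.

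**Filter.** The pre-processing list in Protocol 7.3 removes genes with high pre-treatment variability: "A gene is excluded if it meets the regular criteria (>1.5 fold deregulation, FDR adjusted p value <0.01", tested between V1b and V2 only. SAP 7.4 takes over this pre-processing by reference.

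**Baseline.** Protocol 7.3.1: "Only one baseline value is included in the model, namely the last value before first drug administration". That is the V2 pre-dose sample.

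**Role of the two baselines.** Protocol 3.2: "The comparison between two baseline visits will describe the spontaneous variability in expression of the target genes and markers". Protocol 7.1 calls the two pre-treatment samples an internal control.

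**Scale.** SAP 7.4 introduces the definition with "The FDR adjusted P-value based on the Wald test and the log2 fold change, are used to identify deregulated genes". Protocol 7.3.1 has the parallel sentence without log2: "the FDR adjusted P-value based on the Wald test and the-fold change, are used to identify deregulated genes".

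**Outputs.** The visible SAP 7.4 reports counts for post-baseline time points. Its sensitivity list varies the analysis set and the FDR threshold, but not the fold cut.

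**The concern.** The filter refers to *regular criteria*, but its 1.5-fold cut matches no criterion in either document. Only the FDR level agrees. The effect is asymmetric: a significant 1.4-fold change without drug is tolerated, while the same change after dosing counts toward the primary endpoint. With a single arm, the V1b-V2 comparison is the only protection against counting spontaneous change as drug effect. A gene displaced at V2 that returns to its V1b level moves away from the one baseline in the model, and so looks like a response.

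A smaller matter is notation. Absolute-value bars do nothing on a plain positive ratio, and the sign convention for a decrease is not written. The stray log2 in the SAP adds to the untidiness.

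**Working it through.** The documents give no figure that depends on these cuts, so there is nothing to reproduce. The exact part is scale conversion. The rest is illustrative, because no SD is given.

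**Inputs.** From the documents: 10 patients (Protocol 7.7), FDR level 0.01, cuts of 1.3 and 1.5. Assumed: SD of the within-patient log2 difference between two visits from 0.2 to 0.6, a normal approximation, and a true untreated shift of 1.4-fold.

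**Step 1, scale.** log2(1.3) = 0.379; log2(1.4) = 0.485; log2(1.5) = 0.585; 1/1.3 = 0.77.

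**Step 2, significance thresholds.** Under Benjamini-Hochberg at 0.01, the raw cutoff is 0.01 times the share of tested genes declared significant. Raw p < 0.001, 0.0001 and 0.00001 thus correspond to shares of 10%, 1% and 0.1%. The two-sided z values are 3.29, 3.89 and 4.42.

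**Step 3, where the two cuts can differ.** SE = SD/√10. A fold cut adds something beyond significance only if SD < log2(cut) × √10 / z. For 1.5-fold this gives 0.585 × 3.162 / z = 0.56, 0.48 and 0.42. Above those SDs the 1.3 and 1.5 filters are the same filter.

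**Step 4, chance that the filter removes the gene.** P(|estimate| > max(log2 cut, z × SE)). Example at SD 0.3, p < 0.001: SE = 0.0949 and z × SE = 0.312, so the fold cut decides.
- 1.3 cut: Φ((0.485 − 0.379)/0.0949) = Φ(1.13) = 87%.
- 1.5 cut: 1 − Φ((0.585 − 0.485)/0.0949) = 1 − Φ(1.05) = 15%.

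Removal, 1.3 cut vs 1.5 cut:

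| SD | p<0.001 | p<0.0001 | p<0.00001 |
|---|---|---|---|
| 0.2 | 95% vs 6% | 95% vs 6% | 95% vs 6% |
| 0.3 | 87% vs 15% | 87% vs 15% | 76% vs 15% |
| 0.4 | 71% vs 22% | 48% vs 22% | 28% vs 22% |
| 0.5 | 41% vs 26% | 21% vs 21% | 9% vs 9% |

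**Step 5, chance that the gene is counted post-dose.** Simulation with 2,000,000 draws of the V1b, V2 and post-dose means. The shift is at V2 only, there is no drug effect, and V2 is shared by both contrasts. A gene is counted if it survives the filter and its post-dose change is significant and at least 1.3-fold.

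Counted, 1.5 filter vs 1.3 filter:

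| SD | p<0.001 | p<0.0001 | p<0.00001 |
|---|---|---|---|
| 0.3 | 73% vs 8% | 73% vs 8% | 62% vs 13% |
| 0.4 | 51% vs 14% | 32% vs 17% | 16% vs 14% |
| 0.5 | 24% vs 16% | 12% vs 12% | 6% vs 6% |

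At SD 0.6 the two filters agree at every threshold.

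**Step 6, unequal thresholds.** The filter contrast may have fewer significant genes, and so a stricter raw cutoff. With p < 0.00001 in the filter and p < 0.001 post-dose, the results are 73% vs 17% at SD 0.3 and 51% vs 46% at SD 0.4.

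**Step 7, no true shift at V2.** At p < 0.001 the chance of being counted is about 0.007% at SD 0.3 and about 0.10% at SD 0.5, under either filter.

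**The case against.** The filter can be programmed exactly as written: cut, FDR level, test and visits are all stated. Its declared purpose is to remove genes with high variability, so a stricter cut than the endpoint rule could be deliberate, and nothing obliges the two to be equal. The figures need a gene with a real mean shift over about a week without drug, followed by full reversion. No document says that such genes exist or how variable they are. All of this stands. It limits the size of the point but does not remove the mismatch: the filter claims to apply the regular rule, the regular rule is 1.3, and no reason is given for 1.5.

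Two stronger readings are tempting and should not be drawn. First, a reader might infer from the SAP sentence that the cut is 1.3 on the log2 scale. The documents do not support that. The number is attached only to the fold change in the formal definition, SAP 7.4 defers to Protocol 7.3.1, and the Protocol sentence has no log2. Both directions are evidently meant, since Protocol 7.3.1 describes a significant result as "meaning an adjusted mean value clearly lower or higher compared to baseline". Second, a reader might infer that the SAP forgot the V1b-V2 count. Parts of the SAP are not visible here, so that cannot be said. Showing the count is a suggestion.

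**Conclusion.** The mismatch between the filter and the definition is certain from current text. Its effect on the primary count is not known: the percentages apply to a gene that behaves as assumed and do not say how many genes do. Given a true, reverting 1.4-fold untreated shift, the choice of cut matters materially only for low-variance genes, with a paired log2 SD of about 0.4 or less. The gap is large at every threshold examined only at about 0.3 or less. A reader might go further and call the gene count invalid or inflated by a known amount. The documents do not support either claim. The trial is exploratory, tests nothing in a confirmatory sense, and attaches no decision rule to the count. The point is worth correcting because the count is the primary endpoint of an uncontrolled trial. The log2 wording and the unwritten sign convention are editorial.

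**What to change.** 1. In the Protocol 7.3 pre-treatment filter, use the same rule as the endpoint (1.3-fold, FDR-adjusted P below 0.01). If 1.5 is deliberate, delete the reference to regular criteria, give the reason, and add the 1.3 filter as a sensitivity analysis in SAP 7.4.
2. Report the number of genes that meet the 1.3 rule between V1b and V2, counted before filtering, beside the post-dose counts as the no-drug reference, unless a section not visible here already plans it. Add a note that this interval is nominally only 6 to 8 days and may understate spontaneous change by Week 8 or Week 12.
3. In SAP 7.4, delete log2 from the introductory sentence. In Protocol 7.3.1 and SAP 7.4, write the rule as ratio ≥ 1.3 or ≤ 1/1.3, that is |log2 fold change| ≥ 0.379.

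**Cost.** Wording in the sections named and one table column, plus a rerun of the counts if 1.3 becomes a sensitivity analysis. The V1b-V2 contrast is already run for the filter, so no new samples are needed. The downside of a 1.3 filter is that somewhat more genes are excluded, so the primary count may be slightly smaller.
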